### **Process evaluation consent**

Participants (and their carers if the patient wishes) local site propel trained HCPs, managers, central intervention delivery team and central team supervisors, who are approached to take part in process evaluation interviews will undergo a consent process with a researcher from the central team or by the site PI or their trained delegee. Participant information sheets, appropriate to the role in the study will be provided and will be available in electronic format and can be printed. The PROPEL team will ensure any completed consent forms completed by the central team researcher are returned to the recruiting site where possible, or stored securely at the PROPEL trial office.

## **4.3 Baseline**

Primary and secondary outcome data will be collected prior to randomisation. Participant demographics, medical history and intended treatment pathway will be collected at baseline. A baseline participant questionnaire, with questions on health-related quality of life, and a 24hour dietary recall will be completed prior to randomisation.

## **4.4 Randomisation**

Before randomising a participant, written informed consent must have been obtained and confirmation of trial eligibility documented in the patient's medical notes. Baseline assessments should also have been completed prior to randomisation. Where a participant is not eligible to proceed to randomisation post informed consent (i.e. if bone marrow results do not confirm remission), this information should be captured on the screening log.

Randomisation should occur at the end of induction chemotherapy, once remission status has been confirmed, and prior to the first cycle of consolidation chemotherapy.

Sites should log on to the PROPEL randomisation portal to randomise the participant. Sites should access the portal via the link below:

**Patients can be randomised via the PROPEL database:**

<https://ctu.warwick.ac.uk/PROPEL>

In the unlikely event the randomisation portal is not available, please contact the dedicated WCTU registration/randomisation line on [name] (Mon-Fri 9am-5pm) excluding bank holidays & Christmas closure.

As part of the randomisation process, the participant will be assigned a unique trial number (TNO) that will be used to identify the participant and be recorded on all CRFs and on any correspondence with the PROPEL Trial Office.

Automated confirmation of the participant's randomisation details, TNO and trial arm allocation will be sent by email to the PI and main contact for the site research team (unblinded).

#### **4.4.1 Method of Implementing the Trial Arm Allocation**

Participants will be randomised on a 1:1 basis to best practice usual care (BPUC) or a personalised prehabilitation care package (PPCP). Trial arms will be allocated randomly using a computer minimisation algorithm held centrally at the Warwick Clinical Trials Unit and stratified by the following variables:

- age (<= 60; >60 years)
- baseline fatigue (none, mild, moderate, severe)
- performance status (Karnofsky performance status: 100-80; 70-50; 40-0) (17)
- intention to proceed to HSCT (yes; no).

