### **8.2 Statistical analysis of efficacy and harms**

#### **8.2.1 Statistics and data analysis**

A detailed statistical analysis plan (SAP) will be produced to provide full details of all statistical aspects of the study. All analyses and reporting of outcomes will be in accordance with CONSORT [52], with primary analysis conducted according to randomised allocation and intention to treat principles.

The primary analysis will be a pragmatic comparison of the PPCP versus BPUC on an intention to treat basis to preserve randomisation and avoid bias. Sensitivity analyses will investigate the effect of the personalised nature of the intervention on any treatment effects and the effect of compliance using a complier averaged causal effect (CACE) analysis.

All measures will be scored according to the appropriate scoring manual and summary measures obtained for each timepoint. A longitudinal mixed effects regression model will be used to estimate the effect of the intervention compared to standard care on fatigue adjusted for patient-level factors including age, performance status and treatment received. The specialist that delivers the interventions will also be considered for inclusion as a random effect in the model although we expect the variation to be negligible due to the large number of specialists across sites. The effect of red cell transfusion use on the outcome will be considered as time-dependent effect, considering haemoglobin levels and timing of transfusions, as anaemia is a universal complication in AML. The individual need, compliance and intensity of the intervention including the number and amount of each component delivered will be investigated and their need for inclusion in the mixed effects regression model evaluated. Exploratory analyses will investigate intervention and covariate interactions to identify any subgroups where the intervention may work differently to the whole population.

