Similar longitudinal analyses will be performed for the secondary QoL outcomes. Time to event outcomes, including the overall survival and relapse-free survival, will be assessed using Kaplan-Meier curves and compared across trial arms using Cox proportional hazards models, adjusted for the stratification factors. The impact of fatigue on these time to event outcomes will also be evaluated using Cox models. Completion of consolidation treatment plan including chemotherapy and HSCT, readmissions to hospital, ICU admission, number of transfusions, complications of HSCT will be compared across trial arms using logistic regression models. Adverse events and serious adverse events will be tabulated and compared if appropriate.

A sensitivity analysis will be considered to determine the degree to which the conclusions may change with different missing data assumptions and mechanism models.

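### The covariates named for the primary fatigue model omit two of the four minimisation factors, baseline fatigue and HSCT intention; fitted as listed, the test would be conservative

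*Protocol*

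**What the plan says.** Protocol section 4.4.1 sets the allocation: "Participants will be randomised on a 1:1 basis", by a central minimisation algorithm on four factors:

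- "age (<= 60; >60 years"
- "baseline fatigue (none, mild, moderate, severe"
- "performance status (Karnofsky performance status: 100-80; 70-50; 40-0"
- "intention to proceed to HSCT (yes; no"

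Section 8.2.1 then sets the primary analysis: "A longitudinal mixed effects regression model will be used to estimate the effect of the intervention" on fatigue, "adjusted for patient-level factors including age, performance status and treatment received". Two of the four minimisation factors appear there. Baseline fatigue and HSCT intention do not.

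For overall and relapse-free survival the same section is explicit: the arms are "compared across trial arms using Cox proportional hazards models, adjusted for the stratification factors". The logistic models for treatment completion, readmission and similar outcomes carry no statement on adjustment.

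Section 4.3 has primary outcome data collected before randomisation, so the baseline fatigue score should be available for the participants who are randomised.

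**The concern.** Minimisation makes the arms more alike on its factors than simple randomisation would. If a factor predicts the outcome, the treatment estimate then varies less from trial to trial. A model that leaves the factor out does not see this: it counts the variation due to the factor as residual noise and reports a standard error for a less balanced design. The confidence interval is too wide and the test rejects less often than its nominal level.

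Baseline fatigue is the starting value of the primary outcome, so some correlation with later fatigue is to be expected. The named covariate closest to HSCT intention is treatment received. That is known only after randomisation and is not the factor on which the arms were balanced, so it cannot stand in for it.

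What is at stake is the width of the interval and the true level of the test for the main result. The protocol also gives its secondary survival models a clearer link to the allocation scheme than its primary model.

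**Working it through.** **Inputs from the protocol (section 8.1).** 300 per arm, standardised difference 0.3, two-sided 5%, 90% power, 20% dropout, sized by a two-sample t-test.

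**Assumption.** The correlation r between baseline and follow-up fatigue is not given. The main range used is 0.3 to 0.6, with 0.7 as an extreme.

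**Step 1: reproduce the stated size.** n per arm = 2 × (1.960 + 1.282)² / 0.3² = 233.5, so 234. Dividing by 0.8 gives 293 per arm, 586 in total (588 by the exact t calculation). This agrees with the stated 600 to within 3%. With 300 × 0.8 = 240 evaluable per arm, SE = √(2/240) = 0.0913 in SD units, 0.3/0.0913 = 3.286, and power = Φ(3.286 − 1.960) = 90.8%.

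**Step 2: omit baseline fatigue after balancing on it.** Let f = √(1 − r²). This treats the balance as complete, at one follow-up time.

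- Reported SE relative to the true SE: 1/f
- Actual level of the nominal 5% test: 2 × [1 − Φ(1.96/f)]
- Power with the factor omitted: Φ[(3.286 − 1.96)/f]
- Power with the factor adjusted for: Φ(3.286/f − 1.96)

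| r (assumed) | f | SE ratio | Actual level | Power, omitted | Power, adjusted |
|---|---|---|---|---|---|
| 0.3 | 0.954 | 1.05 | 4.0% | 91.8% | 93.1% |
| 0.4 | 0.917 | 1.09 | 3.3% | 92.6% | 94.8% |
| 0.5 | 0.866 | 1.15 | 2.4% | 93.7% | 96.7% |
| 0.6 | 0.800 | 1.25 | 1.4% | 95.1% | 98.4% |
| 0.7 | 0.714 | 1.40 | 0.6% | 96.8% | 99.6% |

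**Step 3: check by simulation.** Minimisation on four factors was simulated with a biased coin of 0.8, 480 evaluable participants and one follow-up time. Fatigue was balanced in four categories and HSCT intention had no effect on the outcome. One model fitted age and performance status only; the other added HSCT intention and the continuous baseline score. There were 1000 null runs, and 600 runs at an effect of 0.3, for each r.

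| r (assumed) | Mean reported SE vs true SD, omitted | Level, omitted | Level, adjusted | Power, omitted | Power, adjusted |
|---|---|---|---|---|---|
| 0.3 | 0.091 vs 0.091 | 4.3% | 5.9% | 91.0% | 92.2% |
| 0.5 | 0.091 vs 0.081 | 2.1% | 5.4% | 94.2% | 97.3% |
| 0.7 | 0.091 vs 0.069 | 1.0% | 5.3% | 96.8% | 99.7% |

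With 1000 null runs the Monte Carlo standard error of a 5% rate is √(0.05 × 0.95/1000) = 0.7 percentage points, so the adjusted levels are compatible with 5%. The simulation supports the formulas although fatigue is balanced only in categories. At r = 0.3 the excess in SE is too small to show clearly at this number of runs.

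**The case against.** A reader might infer that the primary model leaves baseline fatigue out and that its standard errors are therefore wrong. The protocol does not support that, for two reasons, and both stand. First, the covariate list is introduced as a set of examples, and full detail is deferred to a SAP that is not at hand; the text shows that the two factors are not named, not that they are excluded. Second, the model is longitudinal and the questionnaire booklet is scheduled at baseline, so baseline fatigue may enter as the first response, which would recover most of the precision. The protocol does not say which form is meant.

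Nor can baseline fatigue be called the strongest predictor on the documents' evidence. That is plausible for a starting value of the outcome, but no figure supports it, and nothing quantifies any effect of HSCT intention.

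The consequence is also limited. The error is conservative, the trial was sized on an unadjusted t-test, and power stays above 90% throughout. The figures describe one time point and assumed correlations, whereas the planned model has repeated measures. At r = 0.3 the loss is small.

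What the objection does not remove is the mismatch in the text. The protocol does name covariates for its primary model, and they do not match its own allocation scheme, while the survival models are tied to that scheme. A SAP written faithfully from section 8.2.1 could omit both factors without contradicting the protocol.

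**Conclusion.** The point holds as a mismatch worth correcting, not as a demonstrated flaw in the primary analysis. Baseline fatigue and HSCT intention are minimisation factors that the primary model does not name.

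If only the named covariates are fitted and baseline is not a response, the standard error is about 5% to 25% too large for assumed correlations of 0.3 to 0.6. The test level is then about 4.0% to 1.4%, and power about 92% to 95% against 93% to 98% when adjusted. False positives are not inflated, the planned 90% power is met either way, and the sample size need not change. What would be lost is precision, and an interval of the right width, for the main result. The size depends on a correlation that the protocol does not give.

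**What to change.** State in Protocol section 8.2.1, and carry into the SAP, that the primary fatigue model and the longitudinal secondary models adjust for all four minimisation factors. Enter the baseline score of the outcome (the FACIT-F fatigue subscale for the primary) as a continuous covariate, or model baseline as a response with a common mean across arms, and say which. Use HSCT intention as recorded at randomisation, not treatment received, as the minimisation factor in the model.

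The same factors can be applied to the logistic models, in line with the survival models. Entering age as continuous is optional.

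The cost is one sentence. The baseline score is already scheduled before randomisation and the other factors are needed to randomise, so no data collection or sample size changes. The sentence should be fixed before unblinded outcome data are seen.

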#### **4.5 Allocation concealment**

Where possible, participant allocation should be concealed from the practitioners conducting the physical outcomes assessments throughout the trial. The practitioners conducting the physical outcomes assessments therefore should be different staff members to those supporting the intervention delivery. To maintain this allocation concealment, sites will divide staff members into two groups: 1) Those who support and deliver intervention and/or control (local intervention HCP); 2) Those who conduct physical outcome assessments (blinded physical outcomes assessor). Those in group 1 will be those that are permitted to receive notification at the point of randomisation revealing the participants allocation.

During the physical outcomes assessments, participants will be asked to not reveal their allocation to the assessing practitioner. If, however, an allocation is revealed, the practitioner will record this on the relevant CRF and inform the trial office on [[contact]](mailto:[contact]). If an allocation is revealed, we ask that where possible the practitioner is changed for the next assessment visit in order to maintain blinded outcomes assessments.

Sites may request a blinded ISF for the blinded practitioners to use, which will only contain the documents relevant to their role.

## 4.6 Trial treatments / intervention

Table 1: Control and intervention composition		
	BPUC	PPCP
Timing	Once prior to first cycle of consolidation chemotherapy	Personalised prehabilitation MDT meeting prior to each consolidation chemotherapy cycle +/- prior to HSCT with support weekly throughout chemotherapy. The end of the intervention will be considered as up to 4 weeks following the final MDT.
Interventions	
A single remote 30-minute appointment with a researcher from the central team to discuss strategies for the participant to undertake self-directed prehabilitation using the identified freely available support materials.
 
Participants will continue to receive standard of care prehabilitation normally received as per site practices.
	
Pre-MDT clinical screening: collation of routinely available clinical data and project-specific assessments to inform the personalised prehabilitation MDT meeting.
 
A 60-minute PPCP online prehabilitation MDT meeting with the multidisciplinary specialist hub in presence of person with cancer, a support person (if desired) and upskilled local intervention HCP. This will occur following blood count recovery, where possible, at least 8 days prior to commencing next consolidation cycle. PPCP will not be provided prior to maintenance chemotherapy such as Azacitidine or Cytarabine.
 
Participants will be offered a range of remote support sessions via the central specialist team depending on needs.
 
Where possible, the local HCP will provide a weekly check-in of 15-30 mins per week to the participant to provide behavioural support, discuss challenges and encourage adherence. Remote support from the multidisciplinary specialist hub can be accessed as needed.
 
Participants will continue with PPCP prescription through their cycle and the process then repeats for each cycle of their consolidation chemotherapy +/- HSCT.
 
Participants will continue to receive standard of care prehabilitation normally received as per site practices.
 
At the end of the intervention, all participants will be signposted to relevant locally available resources and freely available online materials.

Support materials	Participant manual that includes signposting to freely available Maggie's Cancer Support online resources covering emotional wellbeing, nutrition, and physical activity.  Standardised researcher script to facilitate call.	Manual for HCPs and for participants (covering emotional wellbeing, nutrition and physical activity and incorporating behaviour change strategies) in addition to access to Maggie's online resources.
Attendees	Participant +/- their nominated support person. A member of the central PROPEL specialist team (not involved in the PPCP where possible).	Participant +/- their nominated support person. Multidisciplinary specialist hub and upskilled local HCP.
Training		All PROPEL practitioners and local intervention HCP will be upskilled in Acceptance and Commitment Therapy (ACT) principles and key behavioural strategies to facilitate behaviour change. This involves a standardised ½ day training for HCPs, HCP support manual, educational video support and access to the multidisciplinary specialist hub for advice.  Psychological Well-Being Practitioners delivering the emotional well-being intervention will receive two days' worth of training on delivering the intervention. They will be offered ongoing regular supervision with a qualified practitioner psychologist for the duration of the trial.

#### 4.6.1 Best Practice Usual Care (BPUC)

Best Practice Usual Care (BPUC) consists of the provision of freely available online or printed information from Maggie's on self-directed prehabilitation on emotional wellbeing, nutrition, and physical activity, facilitated by a 30-minute scripted conversation with a trained member of the central team who, where possible, is not involved in PPCP, given once, before the first cycle of consolidation chemotherapy. This will be *in addition to* any routine referrals, and standard of care prehabilitation already offered at sites and ensures some level of standardisation.

#### 4.6.2 Personalised Prehabilitation Care package (PPCP)

[figure not shown]
The PPCP is based on the NHS personalised care model [25] . The PPCP is underpinned by behavioural science and principles from Acceptance and Commitment Therapy (ACT). It is informed by our patient and carers experiences alongside the best available evidence for effective behaviour change techniques (BCTs) within interventions developed to support people living with cancer and beyond [26-28], and our own experiences of developing interventions in this area [29, 30]. BCTs to encourage engagement and adherence across the components will include goal setting, action planning, behavioural self-monitoring, and problem solving, alongside the promotion of psychological flexibility.

Screening, assessment, and planning of the PPCP will commence prior to each cycle of consolidation treatment, with remote sessions and compliance facilitated for the duration of that cycle of treatment. This process is repeated for each cycle of consolidation chemotherapy +/- HSCT. The end of the intervention will be considered as up to 4 weeks following the final PPCP meeting. PPCP will **not** be provided prior to maintenance chemotherapy such as Azacitidine or Cytarabine. PPCP will be *in addition to* any routine referrals, and standard of care prehabilitation already offered at sites. At the end of the intervention, all participants will be signposted to freely available online materials.

Figure 3 PPCP timeline

PPCP is a cyclical intervention that will mirror the consolidation cycles of chemotherapy undergone by each participant. PPCP should be commenced **PRIOR** to the commencement of any consolidation cycle, but it will continue throughout each cycle.

PPCP consists of a remote online 60 min personalised prehabilitation MDT meeting informed by pre-planning clinical screening. The patient will be provided with a personalised prehabilitation prescription to commence following the meeting and continue throughout the consolidation cycle (where possible) until the next assessment.

\*CORE-10 & Bespoke motivation questionnaire

**The PPCP has four integrated components delivered as one package:**

**Pre-MDT clinical screening:** Clinical Screening involves the collation of routinely available clinical data by the local site team prior to each personalised prehabilitation MDT.

- 1. Past medical history (PMH), current medications, and allergies**
- 2. Nutrition** - Anthropometric measures (weight (kg), height (cm), dietary intake (food diary \* – paper or electronic) & Full blood count and biochemistry results (U&Es, eGFR, LFTs, magnesium, corrected calcium, phosphate, CRP). This will be used to assess risk of refeeding syndrome/AKI/CKD; degree of malnutrition and enteral or parenteral nutrition requirements (out of scope for this study).
- 3. Wellbeing** – CORE-10 [31] is a monitoring tool with items covering anxiety, depression, trauma, physical problems, functioning and risk to self. The measure has six high intensity/ severity and four low intensity/ severity items.
- 4. Motivation** -1 item bespoke questionnaire for each component (exercise, diet, wellbeing) [24]. Three items total.

*\*Food diaries will be completed either on paper or directly onto myfood24, further details on this can be found in the practitioner manual.*

This information will be used to plan the prehab MDT meeting to ensure it is tailored to the participant. Screening will optimise delivery, safety and identify more complex needs, e.g., enteral or parenteral feeding, active psychosis, suicide risk where onward referral to local specialist allied health professional (AHP) services (i.e., physiotherapy, dietitian, psychology or psychiatry) may be required, and therefore PPCP may be inappropriate. Onward referral to local specialist services will be facilitated by the PROPEL specialist and local HCP. The need for a specialist referral in one domain (e.g., nutrition), will not preclude the participant from receiving PPCP remote delivery in the other two domains (e.g., exercise and psychological well-being). If the participant is under the care of, or receiving treatment from a speciality provided as part of the PPCP intervention, this should be discussed with the central team of PROPEL specialists to ensure there is no cross over.

**Personalised prehabilitation MDT meeting:** A remote 60-minute multidisciplinary (MDT) personalised care planning meeting, will be conducted by at least 2 members of a central team of specialists comprising of a psychologist, a CanRehab trained exercise specialist and dietitian. The meeting will be attended by the patient, their local PROPEL-trained intervention HCP (where possible)\*, and a caregiver (if available and wished by the patient). It will be recorded and used to plan the participant's prehabilitation package for areas not requiring specialist referral, in line with the participant's values, needs and preferences. The personalised prehabilitation assessment will occur prior to each consolidation chemotherapy cycle and HSCT with changes made to the PPCP if indicated prior to each cycle.

*\*Where the local intervention HCP is unable to attend the MDT, they are able to request a follow-up conversation with the central PROPEL team for continuity of care.*

**Personalised prehabilitation care plan:** Following the prehabilitation MDT meeting, participants will be provided with their personalised plan for the treatment cycle, which will include advice on nutrition, physical activity and managing their emotional well-being as required. This will be supported by a manual providing further guidance on these areas, and incorporating behaviour change strategies. Additionally, where indicated participants will be offered a range of remote sessions delivered by the central PROPEL specialist team with no local HCP involvement required. PPCP participants will also have access to the Maggie's information provided as BPUC. Further details of each component of PPCP are described below:

**Emotional wellbeing support:** The intervention is informed by Acceptance & Commitment Therapy (ACT), which is particularly suited to cancer contexts [32, 33]. ACT will be delivered in a remotely guided self-help format that has proved effective with other long-term conditions [34]. It comprises of 4 self-help modules (available as podcasts or written material with audio files) that will be sent to participants, with follow-up phone/video calls from a therapist (Psychological Well-being Practitioner). The audio files contain brief centring/mindfulness exercises to correspond with each respective psychological skill. There are up to 5 telephone calls with a therapist; the first a 15-minute introduction call, and each module is followed-up with a 25-minute reflection call to help participants reflect on their experience and of trying the skills in everyday life. The modules contain opportunities for self-reflection and offer several psychological skills that participants can try. They include written materials, and audio files and cover the 4 skills of 'be present'; 'unhooking'; 'follow your values' and 'build a kind relationship with yourself'.

